3.2.3 Criteria

Subjects must have demonstrated either tumor progression or recurrence by any of the radiographic criteria and/or clinical criteria as defined below:

- a. Subjects with progressive non-resectable disease regardless of location in the brain or spine are eligible for this study. Patients with evidence of leptomeningeal dissemination are eligible for this study. Patients do not require biopsy/histologic confirmation at the time of progression or relapse.
- b. Radiographic progression is defined as >40% increase in the product of the three perpendicular diameters of current tumor relative to the baseline measurement (defined as either the initial scan or scan at start of a previous therapy):
length (L) x width (W) x transverse (T) (current scan) $> 1.4 \times L \times W \times T$ (baseline scan), or the development of any new sites of disease independent of the response of the initial tumor.
See section 7.1.2 for methodology for tumor measurement.
- c. Post radiation changes are often seen on post-treatment imaging studies, so that classification of a patient as having progressive disease may require several serial MRI's if the child has received radiation within the preceding 12 months.
- d. Tumor volume includes the entire tumor volume seen on gadolinium enhanced T1 MR imaging plus non-enhancing abnormality seen on T2 or FLAIR. Coronal and axial images will be evaluated.
- e. All tumor cysts will be included in the tumor volume
- f. Clinical progression without radiographic progression includes children with optic pathway gliomas who demonstrate sustained decrease in visual fields and/or acuity in three serial vision examinations. Each of the vision examinations must be performed >2 weeks apart.
- g. Children with previously negative cerebrospinal fluid (CSF) cytology who show evidence of tumor cells in fluid obtained by lumbar puncture can be designated as having progressive disease in the absence of radiographic evidence of progression.

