7.1.2 Tumor Response Criteria on 2 Dimensional Measurements (per Modified MacDonald Criteria)

- a. Complete Response (CR): Complete disappearance of all measurable and evaluable disease. There are no new lesions and no evidence of non-evaluable disease. All measurable, evaluable and non-evaluable lesions and sites must be assessed using the same techniques as baseline. Patients must not be on any steroids.
- b. Partial Response (PR): $\geq 50\%$ decrease over baseline in the sum of products of perpendicular diameters of all measurable lesions. There is no progression of evaluable disease and no new lesions. All measurable and evaluable lesions and sites must be assessed using the same techniques as baseline. The steroid dose at the time of the scan should be no greater than the maximum dose during the first 8 weeks since initiation of therapy.
- c. Stable Disease (SD): Does not qualify for CR, PR, or progression. All measurable and evaluable sites must be assessed using the same techniques as baseline. The steroid dose at the time of the scan should be no greater than the maximum dose used during the first 8 weeks since initiation of therapy.
- d. Progressive Disease (PD): $\geq 25\%$ increase in the sum of products of all measurable lesions over baseline using the same techniques as baseline, **or** clear worsening of any evaluable disease, **or** appearance of any new lesion/site, **or** clear clinical worsening **or** failure to return for evaluation due to death or deteriorating condition (unless clearly unrelated to this cancer).

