7.1.3 Tumor Response Criteria Based on 3 Dimensional Measurements

- a. Complete Response (CR): Disappearance of all measurable and evaluable tumors. There are no new lesions and no evidence of non-evaluable disease.
- b. Partial Response (PR): $> 65\%$ decrease in the sum of the products of the three perpendicular diameters of the measurable tumors relative to the sum of products of initial baseline measurements - $LxWxT$ (current scan) $< 0.65 * LxWxT$ (initial scan). There is no progression of evaluable disease and no new lesions.
- c. Stable disease (SD): Neither sufficient decrease in the product of the three perpendicular diameters to qualify for partial response nor sufficient increase to qualify for progressive disease.
- d. Progressive Disease (PD): $>25\%$ increase in the sum of products of the three perpendicular diameters of the measurable tumors relative to the initial baseline measurement - $LxWxT$ (current scan) $> 1.25 * LxWxT$ (initial

scan) **or** the development of any new sites of disease. As post-radiation changes are often seen on post-treatment imaging studies, classification of a patient as having progressive disease may require several serial MRIs.

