8.0 CRITERIA FOR REMOVAL FROM PROTOCOL THERAPY AND OFF STUDY CRITERIA

8.1 Criteria for Removal from Protocol Therapy

a. Progressive disease

Note: Transient enlargement of enhancing disease with subsequent shrinkage has been reported during poly-ICLC treatment. Because of this, if the patient has progressive disease by the conventional definition above but does not have unacceptable progression by the definitions below, the treating physician and patient have the options of continuing poly-ICLC treatment on this protocol or of discontinuing treatment.

b. Criteria for unacceptable progression: See definitions of tumor progression outlined in section 7.1.3

1. >50% increase in the product of the three perpendicular diameters of initial tumor relative to the initial baseline measurement – LxWxT (current can) $> 1.5 \times$ LxWxT (initial scan), or the development of any new sites of disease independent of the response of the initial tumor. Post radiation changes are often seen on post-treatment imaging studies, so that classification of a patient as having progressive disease may require several serial MRI's if the child has received radiation within the preceding 12 months.

2. Unacceptable worsening of neurological symptoms that cannot be controlled with corticosteroids.

3. Any other radiological or clinical evidence of worsening to the extent that the treating physician feels it is not in the patient's best interest to continue poly-ICLC.

c. Physician determines it is in patient's best interest.

- d. Patient and/or parent/guardian refusal to continue or inability to comply with protocol
- e. Grade 3 or 4 toxicity that does not resolve to Grade 1 within three weeks after interruption of therapy, or recurrent grade 3 or 4 toxicity at a reduced dose level (see section 4.2).

Note: If final analysis confirms a beneficial effect of poly-ICLC, and/or if tumor recurs after withdrawal from poly-ICLC at the end of the 2-year prescribed treatment period, participating subjects may be offered continued treatment with poly-ICLC (subject to drug availability at that time).

- f. Completion of planned therapy.

Subjects who are off protocol therapy are to be followed until they meet the criteria for Off Study (see below). Follow-up data will be required, unless consent is withdrawn, every 3 months for the first year, every 4 months for the second year, every 6 months for the third year, and then yearly thereafter

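### Section 7.1.3 d applies the 2D rule's 25% to volume, so when growth includes length the secondary 3D analysis calls progression at growth that the 2D size rule calls stable

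*Combined protocol and SAP*

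**What the plan says.** **Progression, 2D (section 7.1.2 d, used for primary PFS6).** At least a 25% "increase in the sum of products of all measurable lesions over baseline using the same techniques as baseline". New lesions, worsening of evaluable disease, clinical worsening and some failures to return also count.

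**Progression, 3D (section 7.1.3 d, secondary).** More than a 25% "increase in the sum of products of the three perpendicular diameters of the measurable tumors relative to the initial baseline measurement", written out as a multiplier of 1.25 on LxWxT, or any new site.

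**Progression at entry (section 3.2.3 b).** "Radiographic progression is defined as >40% increase in the product of the three perpendicular diameters of current tumor relative to the baseline measurement", with a multiplier of 1.4. Baseline here is "defined as either the initial scan or scan at start of a previous therapy".

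**Partial response.** In 2D (7.1.2 b), at least a 50% "decrease over baseline in the sum of products of perpendicular diameters of all measurable lesions". In 3D (7.1.3 b), the wording asks for more than 65%, as a "decrease in the sum of the products of the three perpendicular diameters of the measurable tumors relative to the sum of products of initial baseline" value. The formula in that same 3D sentence, however, requires the current product to be below 0.65 times the initial one.

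**Removal from therapy (section 8.1 b).** "Criteria for unacceptable progression: See definitions of tumor progression outlined in section 7.1.3", followed by a separate figure of more than 50% in the three-diameter product.

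**Use of the 3D results.** Objective 1.2.1 is the overall response rate by 3D measurement. Sections 7.1.4 and 9.0 a define that rate as complete response, partial response or stable disease. Section 9.2.1 runs the same analysis on 2D and on 3D.

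**The concern.** An equal percentage on an area and on a volume is not an equal amount of growth, because a given change in diameter moves the volume further. Two of the protocol's other 3D limits sit where a conversion from the 2D limits would put them. The 3D progression limit does not, and nothing in the text explains why.

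This matters because stable disease counts as a response. The boundary between stable and progressive disease therefore largely decides the overall response rate, which is a named secondary endpoint. Section 9.2.1 will produce 2D and 3D rates that are read side by side. A lower 3D rate could be taken as a finding about the tumours when it reflects only where the two limits were set.

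**Working it through.** **Inputs.** 2D progression 1.25 and 2D partial response 0.50, as area ratios (7.1.2). 3D progression 1.25, and 3D partial response 0.35 in words or 0.65 by formula, as volume ratios (7.1.3). Entry 1.40, volume ratio (3.2.3 b).

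**Conversion, all three diameters changing by the same factor.** Volume ratio = (area ratio)^1.5; area ratio = (volume ratio)^(2/3); diameter ratio = (area ratio)^(1/2) = (volume ratio)^(1/3).

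**Step 1: limits in the plan that do match.**
- 2D progression: 1.25^1.5 = 1.398, or +40% in volume. This agrees with the entry limit of 1.40, which converts back to 1.40^(2/3) = 1.251 in area.
- 2D partial response: 0.50^1.5 = 0.354, a decrease of about 65%. This agrees with the wording of 7.1.3 b.

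**Step 2: limits that do not match.**
- 3D progression: 1.25^(2/3) = 1.160, or +16% in area, against +25% in 7.1.2 d.
- Formula in 7.1.3 b: 0.65^(2/3) = 0.750, a 25% decrease in area, against the 50% in 7.1.2 b and against its own wording.

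| Rule | Volume ratio | Area ratio | Growth per diameter |
|---|---|---|---|
| 3D progression, 7.1.3 d | 1.25 | 1.160 | 7.7% |
| 2D progression, 7.1.2 d | 1.398 | 1.25 | 11.8% |
| Entry progression, 3.2.3 b | 1.40 | 1.251 | 11.9% |

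**Step 3: the discordant band.** Under uniform growth, 7.7% to 11.8% per diameter is progression by 3D and stable by 2D size. Example: +10% per diameter gives area 1.10^2 = 1.21 (stable) and volume 1.10^3 = 1.331 (progression). For an assumed 30 mm tumour, the band is about 2.3 to 3.5 mm per diameter.

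**Step 4: growth that is not uniform.** Let s be the share of log growth that lies in L. When volume reaches 1.25, area is 1.25^(1−s):
- s = 0 (in plane only): 1.25, so the two limits coincide.
- s = 1/3 (uniform): 1.160.
- s = 1/2: 1.118.
- s = 1 (L only): 1.00.

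The discordance needs some growth in L and widens as that share rises.

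**Step 5: weight of one child.** With 23 subjects (section 9.1.1), each child in the band lowers the 3D rate by 1/23 = 4.3 percentage points relative to 2D. The documents give no growth distribution from which to predict how many children that would be.

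**Step 6: measurement error (illustration only).** Assume no true growth, one lesion, and independent error of coefficient of variation c on each diameter at both scans. The SD of the log ratio is √6·c in 3D and 2c in 2D, and the chance of false progression at one scan is P(Z > ln(limit)/SD). At c = 5% this gives 3.4% (3D at 1.25), 1.3% (2D at 1.25) and 0.3% (3D at 1.40). At c = 10% it gives 18%, 13% and 8%. At c = 3%, 3D at 1.25 gives 0.12% and 2D gives 0.01%. The values of c are assumptions, not protocol figures.

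**The case against.** The strongest reply is that nothing in the protocol says the 3D limits were meant to be volume equivalents of the 2D limits. That stands. A reader might infer a conversion that was intended and then botched, but the documents show only an unexplained inconsistency. The support from partial response is also weaker than it looks: the wording matches the converted value, while the formula in the same sentence does not.

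A reader might also say that the entry criteria call such growth stable. They do not. Section 3.2.3 has no stable category, measures from an earlier scan, and admits children through new sites, visual decline or CSF cytology. Only the sizes of the thresholds can be compared.

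Nor do 2D and 3D always disagree. With purely in-plane growth the present limits coincide, and with shrinkage in L the order could reverse. Section 7.1.2 d also has clinical routes to progression that 7.1.3 d lacks, so the two could differ even with matched size limits.

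The 50% in section 8.1 b might be read as a third conflicting definition of progression. The note under 8.1 a, however, deliberately sets a second tier of unacceptable progression above the conventional definition. What remains is a cross-reference to 7.1.3 (25%) followed by a different figure.

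Finally, the error rates in step 6 are assumed and at 3% are negligible, so the point does not rest on them. None of this explains why 3D progression alone has a lower limit.

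**Conclusion.** The point holds as an unexplained mismatch within the secondary 3D criteria. On size alone and under uniform growth, 3D progression is called at 7.7% per diameter and 2D progression at 11.8%. Children in that band count as responders in the 2D overall response rate and as non-responders in the 3D rate. The size rests on growth that includes L, and on measured size being what decides progression.

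A reader might infer that the trial's main conclusion is at risk. It is not. PFS6, the two-stage rule and the final test use the 2D criteria, and the stated design reproduces: type I error 0.046, power 0.80, early stopping probability 0.605 against the stated 61%. The 3D rates are reported as estimates with one-sided confidence intervals, and no decision rule uses them. The change is worth making because it protects a named secondary endpoint at little cost.

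**What to change.** 1. For the secondary 3D endpoint analysis only, define progression by size as LxWxT (current) > 1.4 x LxWxT (baseline), consistent with 3.2.3 b and 7.1.2 d. State that this analysis limit does not set removal from therapy.
2. In the same edit, correct the contradiction in 7.1.3 b between a decrease of more than 65% and a formula of below 0.65. The 2D-equivalent formula is below 0.35 times the initial product. This matters for the traditional rate that counts only complete and partial responses.
3. Reconcile 7.1.3 with 8.1 b, which points to the 25% definition and then states more than 50%. Section 8.1 draws on 7.1.3, so an edit made for the analysis must not silently alter the removal criteria. No view is taken on when treatment should stop.

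**Cost.** Two numbers, one clarifying sentence and one cross-reference to settle. Section 7.1.1 already has L, W and T recorded where L can be measured, so no new data are needed. The downside is small: the 3D analysis registers small growth slightly later. For purely in-plane growth, where volume and area ratios are equal, it would call progression at 1.40 while 2D calls it at 1.25.

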7.1.4 Response Assessment

Tumor response will be assessed at 3, 6, 9, 12, 18, 24 months after starting the therapy, as well as at the time of going off study if prematurely. The overall response rate (ORR), defined as the percent of evaluable subjects who experience a complete response or partial response or stable disease, will be determined. The primary endpoint will be progression free survival rate (per MacDonald Criteria) at 6 months after starting therapy. Secondary endpoints also include tumor ORR at 6 months and 2 years after starting therapy and also the duration of the 'good' response. The traditional overall response rate (CR's and PR's only) will also be summarized.

Each subject will be classified according to their "best response" for the purposes of analysis of treatment effect. Best response is determined from the sequence of the objective statuses described above.

Any subject removed from study protocol because of unacceptable progression (see Section 8.1) will be counted as progressive disease in the efficacy analysis.

8.0 CRITERIA FOR REMOVAL FROM PROTOCOL THERAPY AND OFF STUDY CRITERIA

8.1 Criteria for Removal from Protocol Therapy

a. Progressive disease

Note: Transient enlargement of enhancing disease with subsequent shrinkage has been reported during poly-ICLC treatment. Because of this, if the patient has progressive disease by the conventional definition above but does not have unacceptable progression by the definitions below, the treating physician and patient have the options of continuing poly-ICLC treatment on this protocol or of discontinuing treatment.

b. Criteria for unacceptable progression: See definitions of tumor progression outlined in section 7.1.3

1. >50% increase in the product of the three perpendicular diameters of initial tumor relative to the initial baseline measurement – LxWxT (current can) $> 1.5 \times$ LxWxT (initial scan), or the development of any new sites of disease independent of the response of the initial tumor. Post radiation changes are often seen on post-treatment imaging studies, so that classification of a patient as having progressive disease may require several serial MRI's if the child has received radiation within the preceding 12 months.

2. Unacceptable worsening of neurological symptoms that cannot be controlled with corticosteroids.

3. Any other radiological or clinical evidence of worsening to the extent that the treating physician feels it is not in the patient's best interest to continue poly-ICLC.

c. Physician determines it is in patient's best interest.

- d. Patient and/or parent/guardian refusal to continue or inability to comply with protocol
- e. Grade 3 or 4 toxicity that does not resolve to Grade 1 within three weeks after interruption of therapy, or recurrent grade 3 or 4 toxicity at a reduced dose level (see section 4.2).

Note: If final analysis confirms a beneficial effect of poly-ICLC, and/or if tumor recurs after withdrawal from poly-ICLC at the end of the 2-year prescribed treatment period, participating subjects may be offered continued treatment with poly-ICLC (subject to drug availability at that time).

- f. Completion of planned therapy.

Subjects who are off protocol therapy are to be followed until they meet the criteria for Off Study (see below). Follow-up data will be required, unless consent is withdrawn, every 3 months for the first year, every 4 months for the second year, every 6 months for the third year, and then yearly thereafter

8.2 Off Study Criteria

- a. Death.
- b. Lost to follow-up.
- c. Entry into another therapeutic study.
- d. Withdrawal of consent for any further data submission.

9.0 STATISTICAL CONSIDERATIONS

a. The primary goal of this trial is to obtain preliminary estimates of the ability of poly-ICLC to prevent or delay disease progression in subjects with recurrent or newly diagnosed low-grade gliomas. The primary endpoint will be progression free survival rate at 6 months (PFS6) after starting therapy. Progression free survival is defined as the time from starting study therapy to tumor progression, tumor recurrence, death from any cause, or occurrence of a second malignant neoplasm. Tumor assessment for the primary endpoint will be based on modified McDonald's criteria (section 7.1.2). Tumor assessment results obtained based on the 3D measurements will be considered secondary. The overall response rate (ORR) at 6 months will be a secondary endpoint. The ORR will include complete response, partial response, and stable disease (see Section 7.1.4). Time to progression will be documented for all patients who progress.

b. The second goal is to further define the side effects and toxicity of this regimen in these subjects. Secondary endpoints also include tumor ORR at 2 years after starting therapy and also the duration of the good response. Tumor response will be assessed at 3, 6, 9, 12, 18, 24 months after starting the therapy, as well as at the time of going off study if prematurely. Other secondary endpoints also include tumor response rates based on 3 dimension measurements as in section 7.1.3 at 3, 6, 9, 12, 18, 24 months after starting the therapy, progression free survival and overall survival over the course of the study.

c. The third goal will be to examine a series of biochemical determinations (e.g. serum OAS and interferon levels, PKR, phosphorylation state of eIF2a, p21^{waf-1}) as surrogate markers for sensitivity of patients to poly-ICLC. These will be compared to clinical response data. A subset of the proteins involved in apoptosis and signaling pathways will be looked into specifically to assess the effect of the study treatment on these signaling pathway changes. The specific endpoints are:

- Association of baseline levels of proteins (such as OAS, interferon, PKR, phosphorylation state of eIF2a, p21^{waf-1}) in serum, PBMC and/or cerebrospinal fluid with tumor response status at 6 months after treatment with Poly-ICLC.
- Association of baseline levels of proteins (such as OAS, interferon, PKR, phosphorylation state of eIF2a, p21^{waf-1}) in serum, PBMC and/or cerebrospinal fluid with progression free survival.
- Association of changes in levels of proteins (such as OAS, interferon, PKR, phosphorylation state of eIF2a, p21^{waf-1}) serum, PBMC and/or cerebrospinal fluid from baseline with tumor response status at 6 months after treatment with Poly-ICLC.
- Association of changes in levels of proteins (such as OAS, interferon, PKR, phosphorylation state of eIF2a, p21^{waf-1}) in serum, PBMC and/or cerebrospinal fluid from baseline with progression free survival.

9.1: Study Design and Justification of Sample size

9.1.1 This is a single arm study, to determine the radiographic progression free survival (PFS) rate to poly-ICLC in the treatment of children with recurrent or progressive low grade gliomas. The primary endpoint is the progression free survival status at 6 months (PFS6) after starting therapy. The tumor response categories will include complete response, partial response, stable disease or progressive disease, as assessed according to section 7.1.2.

Simon's optimal two-stage design will be used for this study (Simon, 1989). Suppose 50% is the uninteresting level, i.e., if the PFS6 rate is $\leq 50\%$, we will consider the new regimen as not promising. This 50% baseline response rate in the absence of treatment is from historical experience (this rate was also used by the Everolimus study which is a phase II study for recurrent or progressive LLG in children), also taking into account that this study patient population are more refractory. We will test the null hypothesis $H_0: p \leq 50\%$ against the alternative hypothesis $H_1: p > 75\%$, where p is the PFS6 rate. The two stage design proposed below will have 80% power to reject the null and conclude that the true response rate is above 50%, if the true response rate is $\geq 75\%$, at 5% significance level.

The study design can be described in detail as follows:

Stage 1: Fourteen subjects will be accrued; accrual will be held up until the PFS6 results for all the 14 subjects are known. The trial will be terminated at Stage 1 if ≤ 7 subjects have a PFS6 response; otherwise it continues to Stage 2. Note that any subject who goes off study early due to toxicity, will be counted as a non-response (an intent to treat analysis).

Stage 2: Nine more patients will be accrued. We will reject the therapy if among all the 23 (14+9) subjects, the number of patients who have a defined response is ≤ 15 .

Early stopping probability: Under this design, if the null hypothesis is true, the probability of stopping the trial early will be 61%.

9.1.2 Interim analysis and early stopping for efficacy:

The interim analysis will be conducted as soon as the first 14 patients have accrued and are evaluable for the primary outcome. If ≤ 7 subjects had a defined response, the trial will be stopped early for lack of efficacy.

